CLINICAL PROTOCOL

409 **Aim 1.1** the superiority of the PF over Sensor-augmented mode (SAM) in controlling GV. PF is a
410 system designed to provide patients with *actionable information* about glucose control in general
411 and GV in particular (e.g. estimated HbA1c (eA1c), risk of hypoglycemia, and activity level);

412 **Aim 1.2** the superiority of the DSS over SAM in controlling GV. DSS is a CGM-based system that
413 includes PF and further assists with treatment recommendations for common metabolic
414 challenges;

415 **Aim 1.3** the overall non-inferiority of DSS over PF intervention to control GV and superiority of
416 DSS to maintain tight glycemic control over time (lower variations of GV in time).

417 **Aim 2 (personalization of treatment policy)** We hypothesize that the participants in this study
418 will have technology intervention preferences (e.g. PF or DSS) that can be predicted by key
419 psychosocial and behavioral parameters and are prognostic of the level of GV control achievable
420 by the intervention. We will:

421 **Aim 2.1** confirm that technology acceptance and trust are predictive of the level of GV control
422 achieved during the study (see Aim 1), regardless of the type of DSS system in use. We
423 hypothesize that technology acceptance will correlate negatively with GV: i.e. higher technology
424 acceptance leads to lower GV;

425 **Aim 2.2** explore the impact of technology expectations and experience on the performance of
426 each type of technology intervention (SAM, PF, DSS). For example, higher expectation will
427 negatively correlate with GV for the SAM treatment, but not the DSS treatment.

428 **Aim 2.3** assess the correlation between relevant psycho-behavioral traits with the performance
429 of PF vs DSS, identifying potential pathways to the corresponding optimal technology-based
430 treatment policies.

431 **1.3. Outcomes**

432 **1.3.1. Glycemic outcomes**

433 The primary outcome of this study will be Glucose Variability (GV) as measured by CGM-based
434 Coefficient of Variation (CV), as recommended by the International Consensus on Use of
435 Continuous Glucose Monitoring. To further characterize glucose control, we will compute other
436 CGM Consensus outcomes as well:

437 Average

438 Percent in different ranges:

439 ○ <50 mg/dL

440 ○ <54 mg/dL

[figure not shown]
CLINICAL PROTOCOL

- 441 ○ <60 mg/dL
- 442 ○ <70 mg/dL
- 443 ○ ≤70-≤180 mg/dL
- 444 ○ >180 mg/dL
- 445 ○ >250 mg/dL
- 446 ○ >300 mg/dL

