476 experience. This will examine relevant core constructs of trust, acceptance, satisfaction,
477 confidence as well as fear, worries, distress and burden. Validated and reliable measures will be
478 used to explore psycho-behavioral characteristics and outcomes in addition to specifically
479 adapted measures for SAM and DSS technologies to capture holistic, disease-specific and
480 technology-specific data. These questionnaires will evaluate how specific constructs are
481 predictive of successful glycemic outcomes associated with DSS. These questionnaires will enable
482 us to assess important non-glycemic treatment outcomes that are meaningful to patients
483 including those affecting Quality of Life (QOL) (e.g. fear of hypoglycemia and diabetes distress).
484 To those ends, participants will complete a battery of questionnaires related to diabetes
485 management, treatment satisfaction and QOL at baseline (before system use) and after each
486 treatment modality.

487 **1.3.5. Ecological Momentary Assessment Data Collection**

488 Participants will be trained on the EMA surveys and requirements. During each treatment
489 condition, over the course of 2-3 days every two weeks, the participant will be asked to complete
490 a "Daily Diary" with 3-5 entries of 3-4 questions each day, for a minimum total of 48 entries per
491 participant during each Phase. The DiAs phone will display a text message containing a link to the
492 survey. Surveys will be triggered at fixed times, including a morning survey ~1h after waking up
493 and an end-of-the-day survey around 8-9 PM. Participants will be able to delay (up to 30 min) or
494 skip (up to 2 per day excluding at wake up) surveys for their convenience. Participants will
495 respond to questions on a 5-point Likert scale (0=Not at All, 4=Extremely). The first Diary for each
496 day will contain two additional items for rating sleep quantity/quality. The Daily Diary questions
497 are intended to assess agreement, trust, treatment satisfaction, diabetes burden, self-efficacy,
498 mood valence, energy level, physical well-being, and concerns about hypo- and hyperglycemia.
499 The first Diary for each day will contain two additional items for rating sleep quantity/quality.

CLINICAL PROTOCOL

500 **1.3.6. Mapping of Psycho-behavioral Characteristics to DSS Preferences and Performance**

501 Baseline assessments of psycho-behavioral traits will be introduced as covariates in the general

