502 linear model when analyzing the glycemic performance of each treatment modality (SAM, PF,
503 DSS). Contrasts will be used to study each pair, specifically SAM vs any advisory system. For
504 constructs that can be changed by the intervention itself (e.g. Fear of hypoglycemia) and that are
505 therefore measured after each intervention, we will use repeated measures model with within-
506 subject covariates (MIXED models) to understand their impact on DSS efficacy. This analysis will
507 shed light on the relationship between the efficacy of treatment modality and individual patient
508 characteristics; **Aims 2.1 and 2.2**

509 Using the cloud data system, we will isolate patient-system interactions for each advisory module
510 (e.g. eA1c, predictive hypoglycemia alert), and compute for each subject the probability of the
511 interaction to lead to the expected action, and positive glycemic outcomes. These probabilities
512 will then be used as outcome variables in separate analysis to assess whether psycho-behavioral
513 traits are associated with the acceptance of specific advisory functionalities (e.g. Fear of
514 Hypoglycemia could be lowered by the hypoglycemia prediction module); answering **Aim 2.3**.

515 **1.3.7. Identification and Validation of the Acceptance & Trust Index**

[figure not shown]
516 Finally, we will use the validated trust and acceptance measures obtained throughout the
517 protocol to validate the dynamic tracking of ATI. The 80 studied subjects will be divided in 4
518 cohorts of 20, the first 3 groups used to iteratively refine our estimation procedure (interaction
519 quantification and dynamical model parameters) to accurately reproduce acceptance and trust
520 fluctuations. The last group will be used to prospectively demonstrate the correlation between
521 ATI, trust, and acceptance, thereby addressing **Aim 3.2**; retrospectively we will use the finalized
522 method on all 80 participants to compute the auto-correlation between trust and acceptance
523 and ATI and study the ability of ATI to track changes in time; **Aim 3.3**. Such an index, shown to
524 follow the evolution of robustly assessed trust and acceptance (via standard methods) will enable
525 future systems to characterize its interactions with its user, detecting early drop in adherence
526 and disconnect with patient's expectation (fault detection), and potentially associating them with

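### The analysis assigned to Aim 2.3 relates traits to single-module responses and specifies no PF-versus-DSS comparison, so it does not match the aim

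*Combined protocol and SAP*

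**What the plan says.** Section 1.2 states Aim 2.3 as to "assess the correlation between relevant psycho-behavioral traits with the performance" and continues "of PF vs DSS, identifying potential pathways to the corresponding optimal technology-based" treatment policies. The comparison of interest is therefore PF with DSS, and the purpose is to match people to one or the other.

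Section 1.3.6 has two paragraphs of analysis.

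- The first paragraph begins "Baseline assessments of psycho-behavioral traits will be introduced as covariates in the general" and goes on "linear model when analyzing the glycemic performance of each treatment modality (SAM, PF" and DSS). It plans contrasts for every pair of modalities, singling out SAM against the advisory systems. For constructs that the intervention can change, it plans mixed models. Its stated purpose is to relate the efficacy of a modality to patient characteristics. It is labelled as serving Aims 2.1 and 2.2.
- The second paragraph begins "Using the cloud data system, we will isolate patient-system interactions for each advisory module". For each person it computes the probability of the "interaction to lead to the expected action, and positive glycemic outcomes. These probabilities" then become the outcome variables, to see whether "traits are associated with the acceptance of specific advisory functionalities (e.g. Fear of" hypoglycemia being the example). It ends "Hypoglycemia could be lowered by the hypoglycemia prediction module); answering Aim 2.3".

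Section 14.5 adds general linear models of the psychological measures and glycemic outcomes, with group and study phase as covariates. It cites no aim number and names no PF-DSS contrast.

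**The concern.** Choosing between PF and DSS for a given person is a question of effect modification: does the DSS-minus-PF difference in glucose variability change with the trait? The analysis labelled for Aim 2.3 can show that a trait goes with acting on one module, or with a good glycemic result after using it. Neither finding says who does better on DSS than on PF.

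Personalization of treatment is one of the trial's three aims. If no model for it is fixed in advance, any later PF-DSS trait result rests on a model chosen at the time of analysis. It would also be chosen across many instruments: section 9.13 schedules five questionnaires at Visit 1 and three in the last week of run-in, so 5 + 3 = 8 before randomization.

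**Working it through.** The plan gives no power statement or other figure for Aim 2.3, so there is nothing of its own to reproduce. The check is mainly a comparison of texts.

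1. **Quantity the aim needs.** The association of a trait with PF performance relative to DSS performance (section 1.2).

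2. **Quantity the labelled analysis estimates.** The association of a trait with a per-person, per-module probability (section 1.3.6, second paragraph). The unit is the module. No term or contrast sets PF beside DSS.

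3. **Could the modules supply the contrast?** Section 1.1.1 lists eight modules with the modes in which each is active. One (the CGM display and alarms) runs in all three modes. Three (hypoglycemia risk, insulin sensitivity, insulin on board) run in PF and DSS. Four (exercise advice, bedtime advice, smart bolus calculator, treatment parameter optimization) run in DSS only. Those four have no PF counterpart. The modules common to PF and DSS could be compared between phases, but the plan does not say that they will be.

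4. **Does the first paragraph of 1.3.6 supply it?** Write CV for person i in modality m, with trait T, in two ways:
   - Common slope: CV(i,m) = mu(m) + b·T(i) + person effect + error. The DSS-minus-PF difference is then mu(DSS) − mu(PF) plus error, and carries no trait information.
   - Slope by modality: CV(i,m) = mu(m) + b(m)·T(i) + person effect + error. The difference is then mu(DSS) − mu(PF) + [b(DSS) − b(PF)]·T(i) plus error.

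   Aim 2.3 needs b(DSS) − b(PF), which is the trait-by-modality term. The paragraph does not say which form will be fitted, does not name that term, and does not assign it to Aim 2.3. Aim 2.2 has the same need: its example expects expectation to correlate with variability under SAM but not under DSS, which is a difference in slopes.

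5. **What 80 completers could detect.** Section 14.2.1 gives 100 randomized and 20% attrition: 100 × (1 − 0.20) = 80. For a correlation r between one trait and the within-person DSS-minus-PF difference, Fisher's z gives r = tanh[(z for alpha + z for power) / √(n − 3)], with √77 = 8.775.
   - Two-sided 0.05, 80% power: (1.960 + 0.842)/8.775 = 0.319, so r = 0.31.
   - Two-sided 0.017 (the corrected level in 14.2.1), 80% power: (2.387 + 0.842)/8.775 = 0.368, so r = 0.35.
   - At 95% power the values are r = 0.39 (alpha 0.05) and r = 0.43 (alpha 0.017).

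   A correlation of 0.309 means that the trait explains 0.309² = 0.095, or about 10%, of the variance of the DSS-minus-PF difference.

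**The case against.** The strongest reply is that the plan already contains the needed model under another label. The first paragraph of 1.3.6 puts traits into the model of glycemic performance, promises contrasts for each pair (PF-DSS is one of them), and describes its purpose in terms close to effect modification. A repeated-measures general linear model normally gives a between-subject covariate its own slope in each phase, so the slope difference would be available. This largely stands, and it limits the point to one of assignment and specification.

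It also answers two stronger readings that a reader might infer. The first is that Aim 2.3 cannot be answered at all. The documents do not support this, because every participant is scheduled for both PF and DSS and the measurements needed are already planned. The second is that a baseline trait must cancel from every pairwise contrast. That is true only of the common-slope form, which the plan never specifies and which would sit badly with the example in Aim 2.2.

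Two further replies have some force. The module probabilities include positive glycemic outcomes, so the analysis concerns more than acceptance; it remains at module level, however, and still sets no PF result against a DSS result. And Aim 2.3 is worded in an exploratory way, with no power claim. That bears on how serious the mismatch is, not on whether it exists.

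**Conclusion.** The concern holds as a mismatch between aim and assigned analysis. Followed as written, the second paragraph of 1.3.6 answers which traits go with responding to particular modules, not which traits go with doing better on DSS than on PF. The model that could answer the aim sits one paragraph earlier, is assigned to other aims, and leaves its key term unstated.

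The change should be made, but the gap is not critical. The planned modality comparisons for Aims 1.1 to 1.3 in section 14.3.2 specify no trait covariate and are unaffected.

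The figure of r = 0.31 shows what the trial could detect; it does not measure harm. It assumes 80 people with usable CV in both the PF and DSS phases, one trait per test, approximate normality, and no adjustment for testing several traits.

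**What to change.** In section 1.3.6, and in Chapter 14 where Aim 2.3 now has no analysis of its own:

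- Assign to Aim 2.3 a model of phase CGM CV (last four weeks of each phase) with modality, order, the mean-centred baseline trait, and trait by modality. Report the DSS-minus-PF difference in trait slopes with its confidence interval. Centring lets the modality terms be read at the average trait value.
- Use the same interaction for Aim 2.2, reading off the SAM and DSS slopes and their difference.
- Keep the module-level probabilities as a supportive analysis under Aim 2.3, and describe them as such.

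The cost is a few sentences and one more model. No new data, visits or participants are needed.

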1240 aspects of a user's experience regarding automated insulin delivery for both patients and family
1241 members. The surveys include various topics important to patients with T1DM and their family
1242 members based upon >200 hours of qualitative interviews and focus groups. It was adapted by
1243 its developer for use with the PF and DSS. The survey includes 22 items. Response options include
1244 a 5-point Likert scale from strongly agree to strongly disagree, along with an N/A option.
1245 Administration time is approximately 5 minutes.

1246 **9.12. Ecological Momentary Analysis (EMA)**

1247 In addition to the behavioral data automatically recorded (e.g. insulin dosing, interactions with
1248 system), an EMA procedure will be used to track the users' daily experiences of trust in the
1249 system, emotional well-being, treatment satisfaction, and diabetes-related concerns and burden.
1250 Using a brief daily survey, we will capture the dynamic changes in participant experience
1251 throughout the day and the associations between users' subjective experience and their
1252 reactions to/interactions with the PF and DSS devices. This will be the first use of EMA with
1253 decision support systems.

CLINICAL PROTOCOL

1254 During each treatment condition, over the course of 2-3 days every two weeks, the participant
1255 will be asked to complete a “Daily Diary” with 3-5 entries of 3-4 questions each day, for a
1256 minimum total of 48 entries per participant during each Phase.

1257 The DiAs phone will display a text message containing a link to the survey. Surveys will be
1258 triggered at fixed times, including a morning survey ~1h after waking up and an end-of-the-day
1259 survey around 8-9 PM. Participants will be able to delay (up to 30 min) or skip (up to 2 per day
1260 excluding at wake up) surveys for their convenience.

1261 Participants will respond to questions on a 5-point Likert scale (0=Not at All, 4=Extremely). The
1262 first Diary for each day will contain two additional items for rating sleep quantity/quality.

1263 The Daily Diary questions are shown below and are intended to assess agreement, trust,
1264 treatment satisfaction, diabetes burden, self-efficacy, mood valence, energy level, and physical
1265 well-being.

1266 • Quality of Life Parameters

1267 ▪ At this moment, to what extent do you feel...

1268 ➤ Burdened by your diabetes treatment?

1269 ➤ Worried about your blood sugar levels?

1270 ➤ In a positive or good mood?

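### The Aim 3.3 tracking correlation for the Acceptance and Trust Index is computed on 80 participants of whom 60 were used to tune it, so it is biased upward by an amount the documents do not fix

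*Combined protocol and SAP*

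**What the plan says.** Section 1.3.7 of the combined protocol and SAP sets out the validation of the ATI in three steps.

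- **Split and tuning.** "The 80 studied subjects will be divided in 4" "cohorts of 20, the first 3 groups used to iteratively refine our estimation procedure (interaction" "quantification and dynamical model parameters) to accurately reproduce acceptance and trust" fluctuations. What is tuned includes how interactions are scored as well as the model parameters, and the target is trust and acceptance.
- **Aim 3.2.** "The last group will be used to prospectively demonstrate the correlation between" the ATI and the trust and acceptance measures. This is cohort 4, with 20 people.
- **Aim 3.3.** "retrospectively we will use the finalized" "method on all 80 participants to compute the auto-correlation between trust and acceptance" "and ATI and study the ability of ATI to track changes in time".

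No cross-validation, optimism correction or separate reporting of tuned and untuned cohorts is given for Aim 3.3. Chapter 14 has no analysis section for Aim 3 and mentions the ATI only when it discusses escalation against de-escalation. Section 1.2 lists Aims 1 and 2 only, so Aims 3.2 and 3.3 are known from the labels in section 1.3.7.

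**The concern.** An index tuned to reproduce a score will agree with that score, in the people it was tuned on, better than it will in new people. Part of the fit is to chance features of those people's data. Aim 3.3 measures agreement with the same scores in a sample that is three-quarters tuning data, so the expected error is upward.

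The consequence is for the claim that the ATI follows trust over time. Section 1.3.7 intends that claim to support later systems that detect falling adherence and adapt themselves. A correlation on 80 people also looks firmer than one on 20, and calling the analysis retrospective does not tell a reader that most of it is in-sample.

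**Working it through.** **Inputs from the documents.** There are 4 cohorts of 20, so 4 × 20 = 80, which matches the completers in section 14.2.1 (100 × 0.80 = 80). Tuning uses 3 × 20 = 60, and 60/80 = 75%. Section 9.12 gives the diary timing: "During each treatment condition, over the course of 2-3 days every two weeks, the participant" completes diaries. An 8-week phase has four such blocks, so 8 to 12 diary days, or 24 to 36 over three phases. The trust and acceptance items appear only in the last diary of the day, so there are at most about 24 to 36 ratings per person.

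**No plan figure to reproduce.** The documents give no expected ATI correlation, number of tuned parameters or power for Aim 3. The sample size in section 14.2.1 was set for Aim 1.

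**Assumptions.** The number of weights, whether they are shared or person-specific, and whether the correlation is within person, pooled or on one value per person are all assumed. I read the plan's auto-correlation as a correlation between the ATI and the trust and acceptance scores.

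**Approximation.** With no true relation, fitting p weights by least squares on data with d degrees of freedom gives an in-sample correlation near √(p/d). Untouched people contribute about zero, so the all-80 value is near 0.75 × √(p/d).

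- Shared weights, within person, 24 ratings: d = 60 × 23 = 1,380. For p = 5, 0.75 × √(5/1,380) = 0.045; for p = 20, 0.090.
- The same with 36 ratings: d = 60 × 35 = 2,100, giving 0.037 and 0.073.
- Parameters fitted per person, 24 ratings: d = 23. For p = 5, 0.75 × √(5/23) = 0.35.
- One summary value per person: d = 59. For p = 5, 10 and 20: 0.22, 0.31 and 0.44.

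**Simulation with no true relation (mean correlation).**

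| Setting | All 80 | Untouched 20 |
|---|---|---|
| Shared weights (5-20), within person, 24-36 ratings | 0.04 to 0.10 | about 0 |
| 1-5 parameters fitted per person, 24-36 ratings | 0.10 to 0.34 | taken as 0 |
| Shared weights (3-20), pooled over people and time, 24 ratings, intraclass correlation 0.5 to 0.8 | 0.09 to 0.34 | about 0 |
| One summary value per person; 5, 10, 20 weights | 0.21, 0.29, 0.40 | about 0 |

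A second run of the last setting gave 0.42 for 20 weights. The approximation runs slightly high there but gives the same ordering.

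**With a true correlation of 0.5.** For within-person tracking with shared weights, all 80 gives 0.50 to 0.51 and the untouched cohort 0.49 to 0.50, a gap of at most about 0.02. With one value per person and 10 weights, all 80 gives 0.55 and cohort 4 about 0.38 to 0.40, a gap of about 0.15 to 0.17.

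**Precision of the held-out cohort, one value per person.** For an observed r = 0.5, Fisher's z is 0.549 with standard error 1/√(n − 3). At n = 20 the 95% interval is 0.549 ± 1.96/√17 on the z scale, or 0.07 to 0.77. At n = 80 it is 0.31 to 0.65, but that narrower interval would surround a biased estimate.

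**The case against.** The strongest reply is that the plan already protects itself. Cohort 4 is reserved as a prospective test, the all-80 analysis is labelled retrospective, and the primary outcome (CGM coefficient of variation) and Aims 1 and 2 are untouched. Aim 3.3 is also about change over time. If the weights are few and shared and the correlation is within person, the bias is small. All of this stands. It limits the size and reach of the problem but does not remove it, because the plan neither separates tuned from untuned people in Aim 3.3 nor commits to the favourable model.

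A reader might infer three stronger things that the documents do not support.

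- *That an unrelated index would show a correlation of 0.2 to 0.4.* The figures of 0.21 to 0.40 come from one value per person, which has no time dimension. Pooled or person-specific fitting can also give values above 0.2, but the documents specify neither.
- *That tracking has no clean test at all.* Section 1.3.7 does not say whether the Aim 3.2 correlation is across people or over time. Cohort 4's time series are in any case among the 80 and can be reported alone.
- *That refitting with each cohort left out would make all 80 fully out-of-sample.* The scoring of interactions was itself refined on cohorts 1-3, and refitting parameters does not undo those choices.

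**Conclusion.** The concern holds. As planned, the Aim 3.3 correlation is scored against the measures used for tuning, in a sample that is 75% tuning data, and it is biased upward. The direction follows from section 1.3.7. The size depends on model choices the documents do not give: from below about 0.10 under no relation, and at most about 0.02 at a true 0.5, for shared weights and within-person tracking, up to 0.3 or 0.4 under less favourable choices. The simulated sizes rest on a linear index fitted by least squares to features fixed in advance. The problem is confined to how the all-80 figure is read; the Aim 3.2 test on cohort 4 is sound.

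**What to change.** For Aim 3.3, report the tracking statistics separately for cohorts 1-3, labelled in-sample, and for cohort 4, labelled held out. Base the tracking conclusion on the held-out figure. If an all-80 figure is shown, state that 60 of the 80 were used for tuning.

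Optionally, refit the parameters leaving out one cohort at a time. Compute the correlation within each omitted cohort, average the four, and use participant-clustered intervals. Averaging matters because pooling the omitted cohorts gave a small negative bias under no relation (about -0.06 to -0.02), against -0.01 to 0.00 when averaged. With one value per person this was more precise than cohort 4 alone (standard deviation 0.13 against about 0.20). State that it corrects for parameter fitting but not for the form of the index chosen on cohorts 1-3, and keep cohort 4 as the prospective test for Aim 3.2.

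The cost is a sentence or two in the plan and, with the option, three more fits beyond the one already made on cohorts 1-3. The interval will be wider and the correlation probably less favourable. No extra participants or data are needed.
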